10.2 Planned recruitment rate

The centres for general practice of KU Leuven, U Ghent, U Antwerp, ULB, VUB and U Liège will each recruit 20 GPs for participation in the trial within a period of 6 months. In case one of the academic centres for general practice fails to reach this goal another centre will be requested to recruit more general practices.

After 3 months, all GPs will have enrolled 10 patients. Taking the high prevalence of BZD use into account there will not be any difficulty in finding enough eligible patients in GP practices included in the study (see 7.1.1 Patient identification).

10.3 Statistical analysis plan

10.3.1 Summary of baseline data and flow of patients

Presentation of baseline characteristics of the study population and comparability of the 2 arms will be based on the following variables:

- Age (mean and standard deviation or median and 25-75 percentiles)
- Gender (percentage)
- Relevant co-morbidities (percentage)
- Benzodiazepine dependence score (means and standard deviation or median and 25-75 percentiles)
- Daily dose of (z)BZD in DDD (means and standard deviation or median and 25-75 percentiles)
- Sleep quality
- Audit-C score

10.3.2 Primary outcome analysis

The primary endpoint will be analyzed according to the intent-to-treat (ITT) approach.

Logistic regression will be used for data analysis with negative benzodiazepine urine test assessed 12 months after initiation of the intervention as a binary outcome and intervention group as a factor. A random effect will be modelled to deal with clustering by general practitioner. The group effect will be reported as an odds ratio with 95% confidence interval.

Subgroup analysis will be performed in order to investigate how the primary outcome behaves in function of:

- age categories
- gender
- (z)BZD dose at baseline in DDD
- Sleep quality at baseline
- Benzodiazepine dependency score
- For the intervention group only: use of e-tool

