7.6 Baseline data

At study entry, the following baseline data will be collected for each participating patient:

- Demographics, comorbidities and medication
- Toxicological screening of urine
- Self-reported use of (z-)BZD (drug name(s), quantity)
- (z-)BZD prescriptions in last 6 months (drug name(s), quantity)
- Audit-C
- EQ5D-3L
- Benzodiazepine Dependence Self-Report Questionnaire
- Insomnia Severity Index
- HLS-EU-Q16

Except for the toxicological screening for which the procedure is explained in 7.7, data will be collected either by completion of the eCRF or via questionnaires sent to the patient.

The invitation to complete the first questionnaire will be sent after signature of the Informed Consent Form (ICF) and registration of the patient in the online platform Slaapzorgeloos/Dormir Sereinement. This first (baseline) questionnaire should thus be completed before the baseline visit takes place. By doing so, we would like to prevent that the patients' answers are influenced by the outcome of the randomisation (see section 7.3.1 *method of implementing the allocation sequence*).

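### The primary and 6-month urine models leave out baseline variables the trial already collects: a small missed efficiency gain, not an invalid test

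*Combined protocol and SAP*

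**What the plan says.** Section 10.3.2 gives the whole primary model: "negative benzodiazepine urine test assessed 12 months after initiation of the intervention as a binary outcome and intervention group as a factor", and "A random effect will be modelled to deal with clustering by general practitioner". Section 10.3.3 applies the same analysis to the 6-month urine test. Neither section, nor 10.3.4, names a baseline covariate or an adjusted sensitivity model. The one covariate-adjusted model in the documents is the cost model in section 10.4, which belongs to a possible later economic analysis outside the trial.

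The variables themselves are collected. Section 7.6 lists demographics, "z-)BZD prescriptions in last 6 months (drug name(s), quantity", the "Benzodiazepine Dependence Self-Report Questionnaire" and the "Insomnia Severity Index". They have two uses:

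- Section 10.3.1, descriptive: "Presentation of baseline characteristics of the study population and comparability of the 2 arms will be based on the following variables".
- Section 10.3.2, subgroups: "Subgroup analysis will be performed in order to investigate how the primary outcome behaves in function of" a list that includes age, "z)BZD dose at baseline in DDD", sleep quality and dependence score.

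Neither use changes the estimated arm effect.

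**The concern.** Practices are randomised, about 120 units if there is one GP per practice, so patient characteristics balance less tightly than under individual allocation of 1200 patients. Section 7.3 stratifies by language and section 4 describes blocks per academic centre; neither controls a patient-level characteristic such as dose or dependence. If such a characteristic is related to discontinuation, leaving it out wastes some precision and leaves any chance imbalance in the estimate.

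Section 10.3.1 will display the comparability of the arms but does not say what follows if they differ. An adjustment settled in advance is more credible than one considered after that table has been seen.

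**Working it through.** **1. The plan's sample size.** Inputs from section 10.1: 15% v 25%, alpha 0.05 (two-sided is assumed; it reproduces the figure), power 80%, 10% loss, ICC 0.11, cluster size 10.

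- n per arm = [1.96√(2×0.20×0.80) + 0.8416√(0.15×0.85 + 0.25×0.75)]² / 0.10² = 250.
- With continuity correction: (250/4)×[1 + √(1 + 4/(250×0.10))]² = 270.
- 270 × 1.1 = 297 per arm, 594 in total.
- Design effect 1 + 0.11×9 = 1.99; 594 × 1.99 = 1182; 1182/10 = 118.2, so 119 GPs.

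This matches the plan exactly. The calculation is not at fault; it simply assumes no gain from covariates.

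**2. Unadjusted power.** Effective number per arm = 1182 × 0.9 / 1.99 / 2 = 267.3. Without continuity correction, power = Φ[(0.10√267.3 − 1.96√0.32)/√0.315] = 82.6%.

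**3. Gain from adjustment.** The documents give no covariate–outcome association, so the strength of one combined baseline score is assumed. Trials were simulated at 15% v 25% with ICC 0.11; the gain is the squared ratio of mean z-values, adjusted over unadjusted.

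| Log-odds per SD (OR) | 120 clusters of 10, no loss, GP-robust logistic, 3000 trials per setting | 120 clusters of 9, exchangeable GEE, 500 trials per setting |
|---|---|---|
| 0.4 (1.49) | 1–2% | not run |
| 0.5 (1.65) | not run | 1–2% |
| 0.6 (1.82) | 4–5% | not run |
| 0.8 (2.23) | 7–8% | 3%, 5%, 6%, 9% at covariate ICC 0, 0.05, 0.1, 0.2 |

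Both estimators stand in for the planned random-effect model. Multiplying 267.3 by 1.01, 1.02, 1.04 and 1.08 in step 2 gives power of 82.9%, 83.3%, 84.0% and 85.4%: a rise of 0.3 to 2.8 points. As a share of 1182 patients, 1–8% is about 12 to 95.

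**4. Chance imbalance.** With 60 v 60 clusters of 10 and covariate ICC ρ (assumed), the SE of a standardised baseline difference is √[(2/600)(1 + 9ρ)].

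| ρ | SE | Chance of a difference above 0.1 SD |
|---|---|---|
| 0 | 0.058 | 8% |
| 0.05 | 0.070 | 15% |
| 0.11 | 0.081 | 22% |

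At ρ = 0.10 the SE is 0.080. A one-SE imbalance shifts the log odds ratio by about 0.4 × 0.080 = 0.03 to 0.8 × 0.080 = 0.06.

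The SE of the unadjusted log odds ratio, with 600 per arm, is √{1.99 × [1/(600×0.15×0.85) + 1/(600×0.25×0.75)]} = √[1.99 × (0.01307 + 0.00889)] = 0.21. The shift is therefore about 0.15 to 0.3 of a standard error.

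**5. Validity.** In 600 simulated null trials the test rejected in 5.7%, within Monte Carlo error of 5% (√(0.05×0.95/600) = 0.9 points).

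**6. When the covariates are measured.** Section 7.7 allocates the practice within a week of the tenth enrolment and holds the baseline visit within 12 weeks of screening. Section 7.6 asks only that the first questionnaire be completed before the baseline visit. A patient may therefore answer it after allocation, although section 7.6 aims to avoid that influence. Age and past prescriptions do not share this problem.

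**The case against.** The strongest reply is that the stated model is a legitimate choice. Section 7.3.1 allocates only after all ten patients are enrolled, the unadjusted comparison is unbiased over randomisations, and its confidence interval already allows for chance imbalance. That stands. A reader might infer that the unadjusted result is biased or its test invalid; the documents and step 5 do not support that.

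Other tempting readings also go too far:

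- *The plan expects discontinuation to depend on these variables.* Listing subgroup factors poses a question. No section states an association, and entry is limited to daily users (section 6.1), which may narrow the range of dose.
- *The gain is 14%, or about 170 patients (0.14 × 1200 = 168), with power rising from 88% to 91%.* That needs the strongest assumed effect (0.8 per SD) together with a quarter of the score's variance lying between GPs, and it ignores loss. Scoring missing outcomes as failures, as section 10.3.4 does, lowers the 14% to 12.5%.
- *Imbalance could move the result by a tenth of the planned effect.* 0.064 is 10% of ln[(0.25/0.75)/(0.15/0.85)] = 0.636, but only at the top assumed strength. The fair yardstick is the standard error, of which it is about 0.3.
- *The baseline data go unused.* They serve the comparability table and the subgroups; they are unused only for adjusting the arm effect.
- *Adjustment will be chosen after the fact.* The documents propose none; they are merely silent.

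Two further objections bear on the remedy: the questionnaire scores may follow allocation, and prescription-based dose misses other sources of supply, as section 3.3 acknowledges. The first requires a timing condition. The second weakens the covariate but does not bias the comparison.

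**Conclusion.** The point holds as a cheap improvement, not as the correction of an error. Arm and a GP random effect are all that the 12-month and 6-month urine models contain, and baseline variables already in hand are left out of both.

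The likely benefit is about 1–8% more effective sample size and roughly 0–3 points of power, with more only if the score also varies strongly between GPs, plus protection against an imbalance shift that would usually be a fraction of a standard error. These figures rest on assumed log-odds of 0.4–0.8 per SD, a covariate ICC near 0.1 for the imbalance figure, and about 120 clusters of ten. With weaker associations the gain is close to nil: at 0.2 per SD it was 0.5%.

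**What to change.** In section 10.3.2, and by reference for the 6-month urine test in 10.3.3, pre-specify these fixed covariates, all continuous:

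- age;
- baseline daily dose in DDD, from the 6-month prescription record, with the window closing before allocation;
- dependence score and Insomnia Severity Index, used only where the questionnaire was completed before the practice's allocation was disclosed and otherwise treated as missing.

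Fill missing baseline values with the overall mean and add a missingness indicator. For the two scores, that indicator is itself settled before disclosure, so it cannot carry an effect of arm. Four covariates are few for about 240 expected events (20% of 1200).

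Keep the unadjusted model as a supportive analysis. The small downside is that the adjusted odds ratio is conditional on the covariates, so report standardised proportions by arm beside it.

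The cost is a short paragraph in the plan, with scoring and timing rules, and a record of each practice's disclosure date against questionnaire completion dates. No extra patient, visit or questionnaire is needed.

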4 TRIAL DESIGN

This study is a pragmatic cluster randomised controlled superiority trial:

multi-centre: 6 academic centres of general practice will be involved in the recruitment of 120 GPs primary care practices

pragmatic: criteria excluding patients from participation will be limited as well as procedures that do not reflect care as usual

cluster: randomisation occurs at the level of the primary care practice while patients are the unit of analysis

randomised: block randomization per academic centre will be performed to assign primary care practices to either the intervention or the control arm

controlled: the intervention will be compared with usual care

superiority: the trial is designed to show that the intervention is superior to usual care

The rationale for choosing a cluster design is to prevent contamination across the intervention and control arm. The cluster and unit of randomization is the primary care practice. There will be 2 arms – the blended care arm and the usual care arm- in 50:50 ratio.

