7.3 The randomisation scheme

In order to avoid contamination between GPs working in the same practice randomization will happen at the level of general practice.

General practices will be randomized in one of the 2 study arms in a 1:1 ratio using a block randomization system stratified per language in order to guarantee that allocation to either usual care or blended care for the discontinuation of (z-)BZD is balanced between communities.

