7.3.1 Method of implementing the allocation sequence

Stratified block randomization will be done using an electronic random numbers generator in blocks of 4 and 6 GPs. Since GPs are only blinded to their allocation until after recruitment of all patients, two block sizes are used to guarantee that the allocation process cannot be predicted. Randomisation and concealment will be centralised at the KU Leuven and conducted by a staff member not involved in data collection or delivering the intervention. Generating the randomisation list will happen in cooperation with a statistician from Leuven Biostatistics and Statistical Bioinformatics Centre.

To avoid cluster heterogeneity and post- randomization selection bias, randomization to either the control arm or intervention arm will be performed only after all 10 patients are enrolled in the general practice. At this time, the study coordinator monitoring the GP's practice will contact the staff member so allocation can take place. The staff member informs the study coordinator and GP as soon as possible of the result.

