10.3.3 Secondary outcome analysis

The proportion of subjects with a negative benzodiazepine urine test assessed 6 months after initiation of the intervention will be analyzed in the same way as the primary endpoint.

All other secondary endpoints are binary variables, measured longitudinally. Analysis will be performed using multilevel logistic regression analysis, including random intercepts for patient and for general practitioner. A random slope for time will be modelled if beneficial for model fit. The fixed effects model will include intervention group, time and the group by time interaction. In case of a significant group by time interaction, the group effect will be reported separately for each time point. In case of a non-significant group by time interaction, a group main effect will be reported. The group effects will be presented as odds ratios with 95% confidence intervals.

The EQ-5D-3L data will be summarized based on the principles of a Pareto improvement in Welfare Economics - the Pareto Classification of Health Change (PCHC) (Devlin 2010). According to this principle an EQ-5D-3L health state is deemed to be 'better' than another if it is better on at least one dimension, and is no worse in any other dimension. And an EQ-5D-3L health state is deemed to be 'worse' than another if it is worse in at least one dimension, and is no better in any other dimension. Using that principle to compare a patient's EQ-5D-3L health states between any 2 time periods, there are only 4 possibilities:

- Their health state is better
- Their health state is worse
- Their health state is exactly the same
- The changes in health are 'mixed': better on one dimension, but worse on another.

The EQ-5D-3L scores will be analyzed as (1) better versus other, and (2) worse versus other.

No correction for multiplicity is planned for the secondary analyses, as the study is not powered for these analyses, and hence, its results will be considered as hypothesis generating.

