10.3.4 Procedure(s) to account for missing or spurious data

See section 7.7 for strategies to maximise follow-up and to prevent missing data.

When a patient withdraws from the study prematurely, all data collected up until the moment of withdrawal will be analysed (using the intent-to-treat approach). In case the data for measurement of the primary endpoint was not collected, the outcome will be classified as failure or continued benzodiazepine use in the intent-to-treat analysis. After withdrawal, no further data of this patient will be collected.

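### Randomisation is stratified, by centre or by language depending on the section, but neither factor is in the primary model, so the confidence interval is too wide if the strata differ

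*Combined protocol and SAP*

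**What the plan says.** Two sections name different stratification factors.

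- **Section 4:** "block randomization per academic centre will be performed to assign primary care practices" to the two arms. There are six centres, which according to section 10.2 "will each recruit 20 GPs for participation in the trial".
- **Section 7.3:** practices are allocated 1:1 "using a block randomization system stratified per language", with the aim of balancing the arms across communities.
- **Section 7.3.1:** "Stratified block randomization will be done using an electronic random numbers generator in blocks of 4 and 6 GPs". No factor is named.

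The analysis uses neither. In section 10.3.2 the 12-month urine result enters a logistic regression "as a binary outcome and intervention group as a factor", with a random effect for the general practitioner. Section 10.3.3 says that the 6-month urine endpoint "will be analyzed in the same way as the primary endpoint". Its longitudinal models have group, time and their interaction as the only fixed effects. Centre and language are also absent from the subgroup list, and no other section adds either to a model.

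**The concern.** Stratified blocks keep the arms nearly balanced within each stratum, so differences between strata largely cancel out of the treatment contrast. A model that omits the stratum does not know this. It places the between-stratum variation in the random effect and counts it in the standard error of the treatment effect. If the strata are prognostic, the reported standard error exceeds the real spread of the estimate.

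What is at stake is power and precision in a trial planned at 80% power. Validity is not threatened. The sample size in section 10.1 takes no credit for stratification, so it is unaffected.

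The mismatch between sections 4 and 7.3 matters even if the strata do not differ. A reader cannot tell which factor the model should carry, and choosing it after outcomes are known would be a data-dependent decision.

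**Working it through.** **Inputs from section 10.1:** control rate 15%, difference 10 points, alpha 0.05 (two-sided reproduces the plan's figure), power 80%, 10% loss, ICC 0.11, 10 patients per cluster. The trial summary gives 120 GPs and 1200 patients.

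**The plan's own figure.** Two proportions, 15% vs 25%, with continuity correction: 270 per arm. 270 × 1.1 = 297, so 594 in total. Design effect 1 + 0.11 × 9 = 1.99, and 594 × 1.99 = 1182. This matches. For 1200 patients the effective number per arm is 1200 × 0.9 / 2 / 1.99 = 271.4. By the same formula this gives 80.3% power, so zb = Φ⁻¹(0.803) = 0.852.

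**Assumption.** The documents give no stratum difference, so gaps around 15% are assumed. The ICC of 0.11 is taken to include the stratum variation.

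**Formulas.**
- Share of variance due to two strata with proportions w and 1−w: share = w(1−w)(pA−pB)² / (0.15 × 0.85). For six centres: variance of the six rates / (0.15 × 0.85).
- True over reported variance: r = [1 + 9(0.11 − share)] / 1.99.
- The reported standard error is too wide by 1/√r − 1.
- Power without the term: Φ(zb/√r). With it: Φ((1.96 + zb)/√r − 1.96).

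| Strata | share | r | SE too wide | Power without → with | Loss (points) |
|---|---|---|---|---|---|
| No gap | 0 | 1 | 0% | 80.3% → 80.3% | 0 |
| Two equal, 12/18% | 0.0071 | 0.968 | 1.6% | 80.7% → 81.6% | 0.9 |
| Two equal, 10/20% | 0.0196 | 0.911 | 4.8% | 81.4% → 83.8% | 2.4 |
| Two equal, 8/22% | 0.0384 | 0.826 | 10.0% | 82.6% → 87.2% | 4.6 |
| Six centres, even over 10–20% | 0.0092 | 0.959 | 2.1% | 80.8% → 81.9% | 1.1 |
| Six centres, even over 8–22% | 0.0179 | 0.919 | 4.3% | 81.3% → 83.5% | 2.2 |

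If language splits 80:40 (assuming four Dutch-language and two French-language centres with 20 GPs each), r is 0.972, 0.921 and 0.846 for the same three gaps, and the losses are 0.8, 2.1 and 4.1 points.

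The formula for r keeps the total variance fixed, which slightly understates the effect. Taking the share directly off the variance of a practice mean gives, at 8/22%, r = 1 − 10 × 0.0384/1.99 = 0.807, and a loss of about 5 points.

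**Simulation, random-intercept logistic model** (maximum likelihood, 120 practices × 9 patients, total ICC 0.11, 3000 trials per cell). At 10/20% the empirical SD of the log odds ratio was 0.238 with or without the term. The mean reported standard error was 0.250 without it and 0.234 with it. Power rose from 84.2% to 85.2% at 12/18%, from 84.9% to 87.5% at 10/20% and from 86.4% to 91.3% at 8/22%. With no gap it was 84.7% and 84.3%. Type I error without the term was 5.0%, 4.7% and 3.3%.

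**Simulation, practice-level analysis with t tests** (120 × 10, two equal strata). At gaps of 6, 10 and 14 points, type I error was 4.3%, 4.1% and 2.9% without the term and 4.8%, 5.2% and 5.1% with it. Power gains were 0.7, 1.7 and 2.9 points.

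**Simulation with GP variation held fixed** (random-effect SD 0.9 on the logit scale, 2500 runs). The standard error was 2–3% too large at 13/19%, 8% at 10/22% and 16–17% at 8/26%. In the last case the mean log odds ratio was 0.705 without and 0.706 with the stratum, and power was 77% vs 86%.

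**The case against.** The case against is mainly about weight. No section says that language or centre predicts discontinuation; section 7.3 gives balance as the purpose. At 8% vs 22%, language alone would account for 0.0384/0.11, about 35% of all between-practice variance, against 18% at 10/20% and 6% at 12/18%. The largest losses therefore need a strong stratum effect. For small gaps the conservatism can hardly be seen: simulated type I error at 12/18% was 5.0% without the term. These points stand, and they keep this an efficiency recommendation.

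A second objection is that a power gain means little unless both tests have the same size. At 10/20% the adjusted maximum-likelihood standard error (0.234) was slightly below the empirical SD (0.238). The practice-level simulation answers this: the adjusted test held 4.8–5.2% and power still rose.

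Third, adjustment is not entirely free. Six centre terms with a plain Wald test gave 6.1% type I error (Monte Carlo standard error 0.4 points), and a t reference on 113 degrees of freedom alone still gave 5.8–5.9%. A practice-level linear model with six centres and the same t reference gave 4.7–4.8%. A small-sample method is therefore needed if centre is the factor.

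Finally, section 10.3.3 treats the secondary results as hypothesis generating, so a slightly wide interval matters less there.

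**Conclusion.** The concern holds. The plan names two stratification factors and models neither. If the strata differ, the primary interval is too wide and some power is lost. If they do not, nothing is lost.

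Over the gaps examined, with the ICC of 0.11 including the stratum variation, the loss runs from 0 to about 5 points of power. This range depends on the gaps chosen. With GP variation held fixed and a gap of 8% vs 26%, the difference reached 9 points, part of which reflects unequal test size (type I error 3.0% without the term and 5.8% with it). The error is in the conservative direction and does not affect the sample size. The change should be made, but the trial remains valid without it.

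**What to change.** 1. Reconcile sections 4 and 7.3, and name in 7.3.1 the factor actually used to generate the list.
2. In sections 10.3.2 and 10.3.3, add that factor as a fixed effect before unblinding.
3. Specify a small-sample correction, for example restricted pseudo-likelihood with Kenward-Roger degrees of freedom. This matters most if the factor is the six centres. A stratified practice-level analysis can serve as a check.
4. Report the unadjusted odds ratio alongside, because the adjusted one is conditional on the factor.

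The cost is SAP wording, a somewhat more careful estimation method and a second odds ratio. Each practice's stratum is known at randomisation, so no patient leaves the model. That includes those without a primary result, for whom section 10.3.4 says "the outcome will be classified as failure or continued benzodiazepine use in the intent-to-treat analysis". Baseline covariates such as dose in DDD or dependence score are not needed for this fix. If they are added, a rule for missing baseline values must keep every patient in the intention-to-treat model.
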